1.5 MODIFICATIONS TO THE STATISTICAL SECTION OF THE PROTOCOL

This section summarizes major changes to the protocol statistical section.

The protocol history table below gives the timing, rationale, and key details of major changes to the protocol statistical section.

The first patient was enrolled on 29-Sep-2016 and the first patient enrolled for Cohort 4 is planned on 01-May-2018.

Table 1 - Protocol amendment statistical changes

Amendment Number	Date Approved	Rationale	Description of statistical changes
1	11-Aug-2016	First step analysis was added to select the dose that will be used in the Phase 3 study	Addition of first step analysis
2	11-Dec-2017	Addition of a cohort (Cohort 4) to further evaluate the every 4 weeks (Q4W) dosing regimen at higher doses (150 mg for body weight <50 kg / 300 mg for body weight \geq 50 kg)	Addition of efficacy and safety analyses for Cohort 4 data including efficacy analyses specific to Cohort 4

1.6 STATISTICAL MODIFICATIONS MADE IN THE STATISTICAL ANALYSIS PLAN

This section summarizes major changes in statistical analysis features made in approved SAP versions, with emphasis on changes after study start (after the first patient was enrolled). The statistical section of the protocol is considered as the first approved SAP.

The statistical analysis plan history table below gives the timing, rationale, and key details for major changes to the statistical analysis features in the statistical analysis plan.

Table 2 - Statistical analysis plan statistical changes

SAP version number	Date approved	Rationale	Description of statistical changes
1	15-Dec-2016	Harmonization of as-treated group definition with previous studies of the project	The alirocumab dose to be used for the as-treated analyses was changed from the dose the patient was treated with the longest duration to the dose the patient was treated with the highest number of injections (see Section 2.3.2).

SAP version number	Date approved	Rationale	Description of statistical changes
2	This version	To assess the efficacy and safety of 150 mgQ4W for body weight <50 kg / 300 mg Q4W for body weight \geq 50 kg	Addition of efficacy and safety analyses for Cohort 4 data including efficacy analyses specific to Cohort 4.
	This version	To better assess the effect of the doses.	Addition of details on the handling of patients who switch to the selected doses for Phase 3.

2 STATISTICAL AND ANALYTICAL PROCEDURES

2.1 ANALYSIS ENDPOINTS

2.1.1 Demographic and baseline characteristics

The baseline value is defined as the last available value obtained up to the date and time of the first investigational medicinal product (IMP) administration in the main phase. For patients included and not treated, the baseline value is defined as the last available value obtained up to the date and time of inclusion.

All baseline safety and efficacy parameters (apart from those listed below) are presented along with summary statistics in the safety and efficacy sections ([Section 2.4.5](#) and [Section 2.4.4](#)).

Demographic characteristics

Demographic variables are gender (Male, Female), race (White, Black or African American, Asian, American Indian or Alaska Native, Native Hawaiian or other Pacific Island, Other), age in years (quantitative and qualitative variable: <10, ≥ 10 to <12, and ≥ 12 years, ethnicity (Hispanic or Latino, Not-Hispanic or Latino).

Medical or surgical history

This information will be coded using the version of Medical Dictionary for Regulatory Activities (MedDRA) currently in effect at Sanofi at the time of database lock.

Medical or surgical history at the time of entry into the main phase will be presented.

Medical or surgical history includes medical history of specific interest such as cardiovascular (CV) history and cardiovascular risk factors other than hypercholesterolemia, subject medical allergic history and family medical allergic history, and relevant medical or surgical history other than CV, CV Risk and allergies. Medical history will be described using all pre-printed terms collected in the dedicated medical history e-CRF pages:

CV history and CV Risk factors history will be based on items pre-listed in the dedicated medical history e-CRF page and include:

- Family history of Myocardial Infarction (MI) (below 50 years of age in 2nd degree relative or below 60 years of age in 1st degree relative)
- Family history of raised cholesterol (>7.5 mmol/L (290 mg/dL) in adult 1st or 2nd degree relative or >6.7 mmol/L (260 mg/dL) in child or sibling under 16 years of age)
- Tendon xanthoma in family (in 1st or 2nd degree relative)
- Familial defective apo B-100

- DNA-based evidence of an LDL receptor mutation (of the subject)
- Tendon xanthoma (of the subject)
- Subject history of raised Total-C (Total-C >6.7 mmol/l (260 mg/dL) in a child under 16 years of age OR >7.5 mmol/l (290 mg/dL) above 16; Levels either pre-treatment or highest on treatment)
- Subject history of raised LDL cholesterol (LDL cholesterol >4.0 mmol/l (155 mg/dL) in a child under 16 years OR >4.9 mmol/l (190 mg/dL) above 16; Levels either pre-treatment or highest on treatment)
- Hypertension (of the subject)
- Type 1 Diabetes (of the subject)
- Type 2 Diabetes (of the subject)

Subject medical allergic history and family medical allergic history will be described using all pre-printed terms collected in the dedicated medical history e-CRF page.

All medical history information, pre-listed or not in the e-CRF, will be coded using the version of Medical Dictionary for Regulatory Activities (MedDRA) currently in effect at Sanofi at the time of database lock.

Disease characteristics at baseline

Specific disease characteristics include:

- Time from diagnosis of heFH (years);
- Confirmation of diagnosis at any time prior to or during the study (genotyping [Yes, No], Simon Broome Criteria [Definite/possible]):
 - If Yes is ticked for genotyping, time of diagnosis will be described (prior to screening, at baseline with centralized genotyping, post-baseline with centralized genotyping);
- Statin intolerant status, as per protocol definition [Yes, No]:
 - If Yes, reason the subject is statin intolerant: [Subject is not receiving a daily regimen of statin/Not tolerating daily dose, Subject unable to tolerate statins, having tried at least 2 statins: one statin at the lowest daily starting dose, AND another statin at any dose, due to skeletal muscle-related symptoms];
 - If Not statin intolerant: [Subject treated with maximal dose of statin he can tolerate due to AE at higher dose [Yes, No]:
 - If Yes, AE(s) encountered at higher doses: [Skeletal muscle related events, Liver function test abnormalities, Co-morbid conditions such as impaired glucose tolerance/impaired fasting glucose, Other].

- Type of lipid-modifying therapy ever taken by subjects age 8 to <10 years (HMG COA reductases inhibitors [statin], fibrates, bile acid sequestrant, cholesterol absorption inhibitor, nicotinic acid and derivates, omega 3 fatty acids \geq 1000 mg/day, other);
- Background lipid modifying therapy at enrollment, as reported in the dedicated prior & concomitant medications e-CRF pages:
 - Atorvastatin daily dose in mg (<10, 10, 20, >20, Other);
 - Rosuvastatin daily dose in mg (<5, 5, 10, 20, >20, Other);
 - Simvastatin daily dose in mg (<10, 10, 20, 40, >40, Other);
 - Pravastatin daily dose in mg (<10, 10, 20, 40, >40, Other);
 - Lovastatin daily dose in mg (<10, 10, 20, 40, >40, Other);
 - Fluvastatin daily dose in mg (<20, 20, 40, 80, >80, Other);
 - Pitavastatin (at any dose);
- Any LMT other than statins
 - Any LMT other than nutraceuticals (by chemical class and drug name) including fenofibrate and ezetimibe or other non-Statin LMT;
 - Nutraceuticals (Omega 3 fatty acids (<1000mg/day), Phytosterols, Psyllium/plantago, Policosanol, Other nutraceuticals);

Other baseline characteristics

Other baseline characteristics include body mass index (BMI) in kg/m² (quantitative and qualitative variable using BMI percentiles defined according to age for boys and girls: <P5: Underweight, \geq P5 to <P85: Healthy weight, \geq P85 to <P95: Overweight and \geq P95: Obesity using the World Health Organization (WHO) growth reference 5-19 years (1, 2, 3), smoking status and alcohol habits.

Efficacy lipid parameters (quantitative variables for all efficacy parameters and the following qualitative variables) will be also summarized at baseline (see definition in [Section 2.1.1](#)):

- Calculated LDL-C: <130, \geq 130 to <160, \geq 160 to <190, \geq 190mg/dL, ie, <3.37, \geq 3.37 to <4.14, \geq 4.14 to <4.91, \geq 4.91 mmol/L;
- HDL-C: <40, \geq 40 mg/dL, ie <1.04, \geq 1.04 mmol/L;
- Non-HDL-C: <160, \geq 160 to <190, \geq 190 to <220, \geq 220 mg/dL (ie, <4.14, \geq 4.14 to <4.91, \geq 4.91 to 5.69, \geq 5.69 mmol/L);
- Fasting TGs: <150, \geq 150 to <200, \geq 200 mg/dL, category \geq 150 mg/dL (mixed dyslipidaemia) will be also displayed, ie, <1.7, \geq 1.7 to <2.3, \geq 2.3 mmol/L;
- Lp(a): <30, \geq 30 to <50, \geq 50 mg/dL, category \geq 30 mg/dL will be also displayed, ie, <0.3, \geq 0.3 to <0.5, \geq 0.5 g/L;
- Apo B: <75, \geq 75 to <90, \geq 90 mg/dL (ie, <0.75, \geq 0.75 to <0.9, \geq 0.9 g/L).

Any technical details related to computation, dates, and imputation for missing dates are described in [Section 2.5](#).

2.1.2 Prior or concomitant medications

All medications taken within 12 weeks prior to screening and until the end of the study, including lipid modifying therapies are to be reported in one of the following specific case report form pages:

- Previous and concomitant statin drugs;
- Previous and concomitant lipid modifying therapies excluding statin;
- Previous and concomitant medications (other than statin, lipid modifying therapies and anesthetic used for any reasons including IMP injection, blood sampling or surgery);
- Topical anesthetic for IMP injection only.

All medications will be coded using the World Health Organization-Drug Dictionary (WHO-DD) using the version currently in effect at Sanofi at the time of database lock.

- Prior medications are those the patient used within 12 weeks prior to screening visit and prior to first OLDFI IMP administration. Prior medications can be discontinued before first administration or can be ongoing during treatment phase.
- OLDFI concomitant medications are any treatments received by the patient concomitantly with the IMP, from first OLDFI IMP to the last OLDFI IMP injection +70 days. For patients entering in the OLE, concomitant medications will be truncated at the day before first OLE IMP injection. A given medication can be classified both as a prior medication and as a concomitant medication.
- Post-treatment OLDFI medications are those the patient took in the period starting from 71 days after the last OLDFI IMP injection. For patients entering in the OLE, post-treatment OLDFI medications will be truncated at the day before first OLE IMP injection.
- In addition concomitant medications for the entire study combining main phase and extension phase (OLDFI/OLE combined period) will be summarized and are defined as any treatments received by the patient from the first OLDFI IMP injection to the last OLE IMP injection (or to last OLDFI IMP injection for patients not entering into the extension phase) +70 days.
- Post-treatment medications for the OLDFI/OLE combined period are those the patient took in the period starting from 71 days after the last OLE IMP injection (or after last OLDFI IMP injection for patients not entering into the extension phase).

Any technical details related to computation, dates, imputation for missing dates are described in [Section 2.5](#).

2.1.3 Efficacy endpoints

Efficacy parameters include lipid parameters (ie, Total-C, calculated LDL-C, measured LDL-C, HDL-C, TGs, non-HDL-C, Apo B, Apo A-1, ratio Apo B/Apo A-1, Lp (a)). All these parameters are measured or calculated by a Central Laboratory, for both scheduled and unscheduled time points. Calculated LDL-C is obtained using the Friedewald formula. Non-HDL-C is calculated by subtracting HDL-C from the Total-C. If TG values exceed 400 mg/dL (4.52 mmol/L), the LDL-C should be measured by the Central Laboratory (via beta quantification method) rather than calculated. All measured LDL-C values provided by the Central Laboratory will not be used for the analysis of calculated LDL-C endpoints.

Unless otherwise specified, all lipid values (scheduled or unscheduled, fasting or not fasting) may be used to provide a value for the efficacy endpoints. All measurements, scheduled or unscheduled, fasting or not fasting, will be assigned to analysis windows defined in [Section 2.5.4](#) [Table 3](#) and [Table 4](#) in order to provide an assessment for time points when the lipid values were to be collected as per protocol. For TGs, only fasting measurements will be used. Measurements with missing fasting status will be excluded from the analyses.

For all time points post baseline, the value used for the analyses at a given time point is the value obtained within the corresponding analysis window.

The baseline value is defined as the last available value obtained up to the date and time of the first OLDFI IMP administration. For patients included and not treated, the baseline value is defined as the last available value obtained up to the date and time of inclusion.

2.1.3.1 Primary efficacy endpoint(s)

The primary efficacy endpoint is the percent change in calculated LDL-C from baseline to Week 8 in the mITT population, using all calculated LDL-C values during the OLDFI efficacy treatment period defined in [Section 2.3.1](#) (on-treatment estimand). Primary endpoint is defined as: $100 \times (\text{calculated LDL-C value at Week 8} - \text{calculated LDL-C value at baseline}) / \text{calculated LDL-C value at baseline}$.

2.1.3.2 Secondary efficacy endpoint(s)

The secondary efficacy endpoints are:

- The absolute change in calculated LDL-C from baseline to Week 8 (on-treatment estimand);
- The percent change in LDL-C from baseline to Week 12 only for Cohort 4 (on-treatment estimand);
- The percent change in Apo B, non-HDL-C, Total-C, Lp(a), HDL-C, TG, and Apo A-1 from baseline to Week 8 (on-treatment estimand);
- The proportion of patients reaching calculated LDL-C <130 mg/dL (3.37 mmol/L) at Week 8 (on-treatment estimand);

- The proportion of patients achieving calculated LDL-C level <110 mg/dL (2.84 mmol/L) at Week 8 (on-treatment estimand);
- The absolute change in Apo B, non-HDL-C, Total-C, Lp(a), HDL-C, TG, Apo A-1, and ratio Apo B/Apo A-1 from baseline to Week 8 (on-treatment estimand).

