7 SELECTION OF PATIENTS

7.1 INCLUSION CRITERIA

Patients meeting all of the following inclusion criteria will be considered for enrollment into the study:

- I 01. Children and adolescent male and female patients aged 8**** to 17 years at the time of signed informed consent.
For Russia only:
Male and female patients aged ≥ 12 and ≤ 17 years at the time of signed informed consent
- I 02. Patients with diagnosis of heterozygous familial hypercholesterolemia (heFH) through genotyping or clinical critiera.*
- I 03. Patients treated with optimal dose of statin** \pm other LMT(s) or non-statin LMT(s) if statin intolerant*** at stable dose for at least 4 weeks.
- I 04. Patients with calculated LDL-C greater than or equal to 130 mg/dL (≥ 3.37 mmol/L) obtained during the screening period after the patient has been on stable LMT (ie, stable optimal dose of statin \pm other stable LMTs or stable non-statin LMTs in statin intolerant patients) treatment for at least 4 weeks.
- I 05. Patients with body weight greater than or equal to 25 kg.
- I 06. Patients aged of 8 to 9 years to be at Tanner stage 1 and patients aged of 10 to 17 years to be at least at Tanner stage 2 in their development.
- I 07. A signed informed consent indicating parental permission with or without patient assent, depending on capacity for understanding based on developmental maturity. In cases involving emancipated or mature minors with adequate decision-making capacity, or when otherwise permitted by law, a signed informed consent directly from patients.

* Diagnosis of heFH must be made either by previous genotyping, current genotyping, or by clinical criteria according to Simon Broome criteria. Previous genotyping refers to documented results that are available from prior genotyping testing supporting a diagnosis of heFH. Current centralized genotyping refers to patients consenting to undergo mandatory genotyping during the screening period with results supporting a diagnosis of heFH. The clinical diagnosis should be based on the Simon Broome criteria for possible or definite FH. (see [Appendix F](#)). Once eligibility is confirmed based on prior genetic testing or Simon Broome criteria, results of elective genetic testing will not impact patient's eligibility.

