7.2.1 Exclusion criteria related to study methodology

- E 01. Age of less than 8 or greater than 17 years at the time of signed informed consent.
- E 02. Calculated LDL-C <130 mg/dL (3.37 mmol/L) during the screening period, after patient has been on stable LMT for at least 4 weeks.
- E 03. Patient without a diagnosis of heFH by genotyping or clinical criteria.
- E 04. Patients aged of 8 to <10 years in whom other available interventions to lower LDL-C have been sufficient.
- E 05. Patients not on a stable dose of LMT (including statin, as applicable) for at least 4 weeks prior to the screening visit and from screening visit to Day 1.
- E 06. Daily dose of statin that is above the maximum recommended dose for pediatric patients as per the local prescribing label.
- E 07. Use of nutraceutical products or over the counter therapies that may affect lipids which have not been at a stable dose for at least 4 weeks prior to the screening visit.
- E 08. Patients not previously instructed on a cholesterol-lowering diet prior to the screening visit.
- E 09. Body weight <25 kg.
- E 10. Patients aged of 8 to 9 years not being at Tanner Stage 1 and patients aged of 10 to 17 years not being at least at Tanner Stage 2 in their development.
- E 11. Patients with secondary hyperlipidemia.
- E 12. Patients with diagnosis of homozygous familial hypercholesterolemia.
- E 13. Patient who has received lipid apheresis treatment within 2 months prior to the screening period, or has plans to receive it during the study.
- E 14. Known history of type 1 or type 2 diabetes mellitus.
- E 15. Known history of thyroid disease.
- E 16. Known history of hypertension.
- E 17. Fasting triglycerides >350 mg/dL (3.95 mmol/L) at the screening visit.
- E 18. Severe renal impairment (ie, eGFR <30 mL/min/1.73 m² at the screening visit).
- E 19. ALT or AST >2 xULN (1 repeat lab is allowed).
- E 20. CPK >3 xULN (1 repeat lab is allowed).

E 21. Patient/parents who withdraws consent during the screening period (patient who is not willing to continue or fails to return).

E 22. Conditions/situations or laboratory findings such as:

- Any clinically significant abnormality identified at the time of screening that in the judgment of the Investigator or any sub-Investigator would preclude safe completion of the study or constrain endpoints assessment such as major systemic diseases.
- Patients considered by the Investigator or any sub-Investigator as inappropriate for this study for any reason, eg,:

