9 ASSESSMENT OF INVESTIGATIONAL MEDICINAL PRODUCT

9.1 PRIMARY ENDPOINT

9.1.1 Primary efficacy endpoint

The primary efficacy endpoint will be the percent change in calculated LDL-C from baseline to Week 8, which is defined as: $100 \times (\text{calculated LDL-C value at Week 8} - \text{calculated LDL-C value at baseline}) / \text{calculated LDL-C value at baseline}$.

The baseline calculated LDL-C value will be the last LDL-C level obtained before the first injection IMP. For patients included and not treated, the baseline value is defined as the last available value obtained up to inclusion.

The calculated LDL-C at Week 8 will be the LDL-C level obtained within the Week 8 analysis window.

All calculated LDL-C values (scheduled or unscheduled, fasting or not fasting) may be used in the analyses if appropriate according to above definition and analysis windows used to allocate a time point to a measurement. Analysis windows will be defined in the Statistical Analysis Plan (SAP).

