The binary endpoint at time point of interest will be derived from observed and imputed lipid values at this time point. Combined estimates for proportion of patients reaching the target for each alirocumab dose groups and for each cohort will be obtained through the SAS MIANALYZE procedure.

2.4.4.2.4 *Summary of results per time point*

For the open-label dose finding treatment period, central laboratory values (in conventional (US) and international units), percent change from baseline, and/or when appropriate absolute change from baseline (in conventional and international units), for calculated LDL-C, Total-C, HDL-C, fasting TG, and non HDL-C at each time point (including Week 10 and W12 time points for Cohort 4), for Lp(a), Apo-B, Apo-A1 and ratio Apo-B/Apo-A1 (absolute change from baseline) at Week 8 time points will be summarized in the mITT population using:

- For lipids other than TG and Lp(a): LS mean and SE for each alirocumab dose group, obtained from the same MMRM models as used for endpoints above and including planned time points (see [Section 2.4.4.2.1](#)) and with raw values, changes from baseline, or percent change from baseline as response variable in the model as appropriate.
- For TG and Lp(a): mean and SE for each alirocumab dose group obtained from multiple imputation approach followed by the robust regression models as used for endpoints above and including planned time points (see [Section 2.4.4.2.2](#)) and with raw values or percent changes from baseline as response variable in the model as appropriate.

In addition, quantitative descriptive summaries by time point (value at visit and % change from baseline) will be presented for all lipids using observed (ie, non-missing) data.

The time profile in %change from baseline of each parameter (except ratio ApoB/Apo A-1 where absolute change will be used) will be plotted according to alirocumab dose received by using LS mean and SE except for TGs and Lp(a). For these 2 parameters, the combined estimate for mean and SE will be used.

For OLDFI /OLE combined period, only quantitative descriptive summaries by time point during the OLDFI/OLE combined efficacy treatment period will be presented for all lipids using observed data in the mITT population. Lipid results pre- versus post-switch to the selected Phase 3 doses will be analyzed separately for Cohorts 1 to 3.

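### The Week 8 proportions below 130 and 110 mg/dL set no baseline condition, so children already below the target before the first injection count as reaching it, with no control arm to offset them

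*SAP*

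**What the plan says.** **Endpoint.** SAP 2.1.3.2 (and Protocol 9.2.1) defines "The proportion of patients reaching calculated LDL-C <130 mg/dL (3.37 mmol/L) at Week 8", with a second endpoint of the same form at 110 mg/dL. SAP 2.4.4.2.3 adds no condition on the starting value: "The binary endpoint at time point of interest will be derived from observed and imputed lipid values at this time point". Results are given by dose group and by cohort.

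**Entry.** Protocol 7.1 (I 04) admits "Patients with calculated LDL-C greater than or equal to 130 mg/dL" on a value from the screening period. The mirror exclusion, E 02 in Protocol 7.2.1, reads "Calculated LDL-C <130 mg/dL (3.37 mmol/L) during the screening period".

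**Baseline.** Protocol 9.1.1 says "The baseline calculated LDL-C value will be the last LDL-C level obtained before the first injection IMP". SAP 2.1.3 agrees: "The baseline value is defined as the last available value obtained up to the date and time of the first OLDFI IMP administration". Normally this is the Week 0 fasting sample, drawn at the dosing visit just before the injection (Protocol 10.1.2.1).

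**Population.** The mITT definition (SAP 2.3.1.1) needs a baseline value to exist. It does not need it to be at or above 130 mg/dL.

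**Baseline table.** SAP 2.1.1 plans the class "Calculated LDL-C: <130" mg/dL. SAP 2.4.1 produces that table on the safety population.

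**The concern.** The value that qualifies a child and the value that serves as baseline are different measurements. The gap can be up to 6 (+1) weeks. For patients screened for Cohort 2 and carried into Cohort 3 it can be up to 3 months without repeat screening (Protocol 6.1). Selection on a single value at or above 130 mg/dL means that some later values will fall below it without any treatment.

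Take a child at 125 mg/dL before the first injection and 129 mg/dL at Week 8. LDL-C rose by 4 mg/dL (4/125 = 3.2%), yet the child counts as reaching the target. In a randomised trial a control arm would carry the same share of such children. Here there is none, so a reader who takes the proportion as an efficacy result cannot tell who was moved below the threshold from who started there.

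**Working it through.** **No figure to reproduce.** The plan gives no expected responder rate, power or baseline LDL-C distribution. The size has to be assessed under assumptions.

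**Inputs from the documents.** Threshold 130 mg/dL (and 110). Entry on a screening value of at least 130. Cohorts of 10, with at least 4 per weight category. Week 8 LS mean changes of -21.2% (Cohort 1), -46.1% (Cohort 2) and -7.7% (Cohort 3), from Protocol section 4.

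**Assumed, not in the documents.** True LDL-C on background therapy, T, is lognormal with mean 170 or 190 and SD 35 or 45 mg/dL. Visit-to-visit CV is 6% or 12%.

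**Model.** Screening S = T×e1, baseline B = T×e2, Week 8 W = T×e3×(1-d). The e terms are independent lognormal with mean 1 and the stated CV, and d is the effect. Only S ≥ 130 enters. There are 2,000,000 draws per setting.

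- Share starting below target: p = P(B<130 | S≥130)
- All-mITT proportion: P(W<130 | S≥130)
- Restricted proportion: P(W<130 | S≥130, B≥130)
- Difference = p × [P(W<130 | B<130) - P(W<130 | B≥130)], within S≥130

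The last line shows why the difference fades at a large effect: both probabilities in the bracket approach 1.

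**Results for 130 mg/dL** (all-mITT % / restricted %):

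| Mean, SD, CV | p | d = 0 | -7.7% | -21.2% | -46.1% |
|---|---|---|---|---|---|
| 170, 35, 6% | 3.7 | 3.7 / 2.2 | 11.8 / 9.2 | 41.3 / 39.1 | 95.5 / 95.3 |
| 170, 35, 12% | 8.0 | 8.0 / 5.5 | 16.0 / 12.5 | 41.6 / 37.5 | 93.5 / 92.9 |
| 170, 45, 6% | 4.3 | 4.3 / 2.5 | 12.5 / 9.5 | 39.2 / 36.5 | 90.8 / 90.4 |
| 170, 45, 12% | 8.8 | 8.8 / 5.6 | 16.5 / 12.1 | 39.4 / 34.4 | 89.0 / 88.0 |
| 190, 35, 6% | 1.2 | 1.2 / 0.8 | 4.7 / 3.9 | 24.0 / 23.0 | 90.7 / 90.6 |
| 190, 35, 12% | 3.3 | 3.3 / 2.5 | 7.7 / 6.4 | 26.4 / 24.4 | 87.9 / 87.5 |
| 190, 45, 6% | 2.1 | 2.1 / 1.3 | 6.9 / 5.4 | 26.8 / 25.2 | 85.6 / 85.3 |
| 190, 45, 12% | 4.7 | 4.7 / 3.2 | 9.8 / 7.6 | 28.0 / 25.1 | 83.5 / 82.7 |

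- Excess at -7.7%: 0.9 to 4.4 points. At -21.2%: 0.9 to 5.0. At -46.1%: 0.1 to 1.1.
- With no drug effect, 27-45% of those below 130 at Week 8 were already below it at baseline.
- Chance of at least one such patient, 1-(1-p)^n: 12-60% in a cohort of 10.
- One patient is 10 points in a cohort of 10 and 25 points in a dose group of 4. For example, 5/10 = 50% becomes 4/9 = 44.4% if one responder started below target.

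**Dose contrast.** The Cohort 1 minus Cohort 3 gap is about 18-30 points either way, and restriction moves it by at most 0.7 points. The Cohort 2 minus Cohort 3 gap widens by 0.7 to 3.3 points, from 72.5-85.9 to 75.2-86.7.

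**110 mg/dL.** 0-1.4% start below the threshold. Restriction changes the proportion by at most 0.9 points at any of the three effects.

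**Wider assumptions.** With normal T (mean/SD 150/30, 170/40, 190/45) and CV 7-15%, p is 2.2-17.3%. The excess is 1.5-5.5 points at -7.7%, 1.7-5.6 at -21.2% and 0.1-1.2 at -46.1%.

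**The case against.** The strongest reply is that these are goal-attainment endpoints. Protocol section 4 gives below 130 mg/dL as the acceptable level and below 110 as ideal, so a child at 129 mg/dL at Week 8 is at goal and is rightly counted. All efficacy analysis is descriptive (SAP 2.4.4), and percent and absolute change are reported separately. This stands as a reason to keep the all-mITT figure. It does not supply the missing information: the endpoint is listed as efficacy, and SAP section 3 says that the efficacy analyses of the dose-finding period support Phase 3 dose selection.

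A second reply is that the baseline table already shows how many started below 130. It does so only as a marginal count, on the safety population, not crossed with Week 8 status. The reader cannot take those children out of the numerator.

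A third reply is that criteria are checked again at the inclusion visit (Protocol 1.3). But I 04 and E 02 refer to the screening-period value, and no rule applies them to the Week 0 sample.

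A reader might also infer that the definition makes weak and effective doses look alike and so distorts dose choice. The check above does not support that, because the gaps between cohorts barely move. Nor do the documents show a decision resting on these proportions: the case for Cohort 4 in Protocol section 4 argues from percent change and individual LDL-C responses.

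**Conclusion.** The gap is real but modest. Under the main assumptions about 1-9% of eligible patients start below 130 mg/dL. The reported proportion is then higher by about 1-5 points at the Cohort 1 and Cohort 3 effects, and by about 1 point or less at the Cohort 2 effect. In any single cohort the effect is lumpy: usually no patient or one, and one patient is worth 10 to 25 points. The 110 mg/dL endpoint is affected much less.

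The primary endpoint does not use the threshold, no test or sample size depends on it, and dose ranking is essentially unchanged. Two further inferences would go too far. The all-mITT proportion is not wrong as a measure of attainment. And restricting to baseline at or above the threshold does not abolish regression to the mean: with no drug effect, 0.8-5.6% of the restricted group would still be below 130 at Week 8. The size rests entirely on assumed distributions, since the documents do not report how many patients had a baseline below 130.

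**What to change.** In SAP 2.1.3.2 and 2.4.4.2.3, and in Protocol 9.2.1:

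- Keep the all-mITT proportion as the goal-attainment endpoint.
- Beside it, by dose group and cohort, prespecify the proportion reaching below 130 (or 110) mg/dL among mITT patients with baseline calculated LDL-C at or above that threshold.
- In the same table, give the number of mITT patients already below the threshold at baseline.
- Run the multiple imputation on all mITT patients as planned and take the subset afterwards. Every mITT patient has a baseline value, so the subset is the same in each imputed data set.

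Protocol section 4 already reports Week 8 results for Cohorts 1 to 3, so the SAP history should record that the row was added after those were known. It can still be fixed before the final dose-finding analysis that includes Cohort 4.

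Cost: SAP wording and one extra row for each endpoint, from data already collected. The added figure has a slightly smaller denominator and will be slightly less favourable. It reduces regression to the mean in the count without eliminating it.
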